7.0 Measurement of Effect

7.1 Pain Response

Assessment of pain should be on a scale of 0 to 10, with boundaries of 0 representing no pain and 10 representing maximal pain. Pain should be assessed by only the worst pain score for the previous 3 days.

Complete response: A pain score of 0 at treated site with no concomitant increase in analgesic intake (stable or reducing analgesics in daily oral morphine equivalent).

Partial response: reduction of 2 or more points (0-10 point scale) without analgesic increase OR analgesic reduction of 25% in daily oral morphine equivalent without increase in pain.

Pain progression:

- Increase in pain score of 2 or more above the nadir at the treated site with stable daily oral morphine equivalent, or
- An increase of 25% or more in daily oral morphine equivalent compared with baseline with the pain score stable or 1 point above baseline

Indeterminate response: Any response that is not captured by the complete response, partial response, or pain progression definitions

All patients with a pain score > 4 in the treated area at the 3-month follow-up will have plain radiographs to assess for bone stability and pathologic fractures.

Any patient with progressive pain in the treated area should have radiographs of the area to assess for bone stability and pathologic fracture.

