3.0 Patient Selection

3.1 Inclusion Criteria

- 3.1.1 Diagnosis of cancer, not including multiple myeloma or lymphoma/leukemia.
- 3.1.2 Radiographic evidence* of bone metastases within 8 weeks of study for non-weight bearing sites and 4 weeks for weight bearing sites. The patient must have pain which appears to be related to the radiographically documented metastasis in the opinion of the treating physician, and the decision has been made by the responsible clinician that a course of palliative external beam radiation therapy is appropriate treatment. Multiple sites eligible if they can be included in no greater than 3 treatment sites and not all identifiable lesions will require treatment unless they are painful lesions

*This should be one of the following: Plain Film, Bone Scan, PET scan, CT scan, or MRI.

- 3.1.3 The involved bone(s) is/are orthopedically stable and not in need of stabilization via either definitive RT, surgical intervention, or both.

- 3.1.4 Eligible Treatment Sites Are:

Weight bearing sites

1. pelvis (*excluding pubis*)
2. femur
3. sacrum and/or sacroiliac joints
4. tibia
5. up to 5 consecutive cervical, thoracic or lumbar vertebral bodies
6. lumbosacral spine

Non-weight bearing sites

7. up to 3 consecutive ribs
8. humerus
9. fibula
10. radius ± ulna
11. clavicle
12. sternum
13. scapula
14. pubis
15. skull
16. bones of hands or feet

If multiple sites are treated, the treatment site is included as weight-bearing if any of the sites include the pelvis, sacrum, femur or tibia.

- 3.1.5 Pain score of at ≥ 5 on a scale of 0 – 10 within a week of enrollment OR pain score < 5 with ≥ 60 mg of morphine (or equivalent) per day.
- 3.1.6 ECOG performance status of 0 - 3.
- 3.1.7 Ability to understand and the willingness to sign an IRB-approved informed consent document.
- 3.1.8 Negative pregnancy test at study registration.
- 3.1.9 Life expectancy of at least 12 weeks as deemed by the treating oncologist.

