4.3 Data Collection

At the time of enrollment, a detailed history and physical exam will be performed, including abstraction of patient vital signs and also documenting co-morbidities, patient demographics, age, gender, other medical conditions, and tumor characteristics. Other variables, such as education level, type of health insurance, and marital status (married/single/widowed/divorced/other) will also be obtained.

Blood Collection: Patients may consent to provide optional blood samples to be used for future genomic studies at baseline.

Prior Cancer Therapy: Information regarding the patient's history for anti-cancer therapy will be recorded.

Use of Bisphosphonates/Denosumab: Information regarding the patient's history for the use of bisphosphonates will be recorded. This will include the specific agent, dose, and date treatment started.

Changes in systemic chemotherapy, hormonal therapy, immunotherapy or the use of bisphosphonates for 4 weeks before and after the delivery of radiotherapy are allowed and will be recorded.

Pain level and Pain Medications: The patient's pain level will be assessed using the NRPS (detailed below). Information regarding the patient's history for the use of pain medications will be recorded. This will include the specific agent, dose, and date treatment started.

Nutrition Status, vitals, BMI: At each encounter, height (at baseline only), weight, Body Mass Index (BMI=kg/M²), and history of weight loss within three months prior to enrollment until patient's study completion will be recorded and/or extracted from patient records.

ECOG Performance Status

Patient Self-Reported Outcomes (SRO):

For evaluation of pain relief, the Numerical Rating Pain Scale (NRPS; Jensen 1999) will be used. The NRPS is a simple measure of pain on an 11-point scale (0-10). In the study comparing the reliability and validity of several measures of pain intensity, the composites of 0-10 ratings have been shown to be useful when maximal reliability was necessary in studies with relatively small sample sizes or in clinical settings in which monitoring of changes in pain intensity in individuals is needed. This will be performed prior to treatment and again at 1, 2, 3, and 6 months.

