5.2 Secondary Outcomes

- 5.2.1 Pain, on a 0-10 scale, and narcotic use, in daily oral morphine equivalents, by treatment arm assessed at 3 and 6 months post-treatment completion.
- 5.2.2 Quality of life by treatment arm, assessed by QLQ-C15-PAL at 3 and 6 months post-treatment completion.
- 5.2.3 Toxicity by treatment arm, assessed by CTCAE version 4.0.
- 5.2.4 Association between patient satisfaction, perceived stress, and social support assessed via self-reported surveys and treatment outcomes.

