11.2 Analysis of Secondary Objective

There are several secondary outcomes of interest in this study. Most of these are measured on a continuous scale (i.e., quality of life by QLQ-C15-PAL, Patient satisfaction with cancer care, perceived stress scale) and thus will be compared between groups using 2-sample t-tests. In addition, the variable for pain response is categorical rather than continuous and will be compared at 3-months between groups using a Fisher's exact test. Patients categorized as Complete or Partial Responders will be compared with those categorized as stable or worsening pain responders.

Groups will also be compared to determine whether there are any differences in the number or severity of toxicities. When comparing severity of toxicities between groups, chi-square tests will be examined. The Cochran-Armitage trend test (in SAS Proc Freq) can be used to determine if there is evidence a trend in severity of toxicities when comparing groups.

In addition to the primary and secondary analyses described above, analyses will be performed that examine whether there are associations between quality of life, patient satisfaction and perceived stress measures and treatment outcome (re-treatment rates or amount of pain relief). In these

analyses, the outcome will be either re-treatment (yes/no) or amount of pain and predictors will include treatment arm, patient level measure and the treatment by patient level measure (i.e., QLQ-C15-PAL) interaction. For these analyses, either multiple logistic regression (for binary outcomes) models or analysis of covariance (ANCOVA) models for continuous outcomes will be used.

In these multiple logistic regression or ANCOVA models additional characteristics such as gender, whether the patient has weight-bearing (yes/no), ECOG performance status, number of lesions, or biophosphonates will also be considered as covariates in the models.

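### Does the overlap between partial response and progression from nadir leave the 3-month pain-response test undefined?

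*Combined protocol and SAP*

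**What the plan says.** Section 7.1 sorts pain outcome into four classes, listed as complete response, partial response, pain progression and indeterminate.

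- The pain limb of partial response reads "Partial response: reduction of 2 or more points (0-10 point scale) without analgesic increase". It names no reference score.
- The first limb of progression reads "Increase in pain score of 2 or more above the nadir at the treated site with stable daily oral morphine equivalent, or" and is followed by a second limb based on a rise in opioid dose from baseline.
- The last class is a residual: "Indeterminate response: Any response that is not captured by the complete response, partial response, or pain progression definitions".

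Section 11.2 says that "the variable for pain response is categorical rather than continuous and will be compared at 3-months between groups" by Fisher's exact test, and then: "Patients categorized as Complete or Partial Responders will be compared with those categorized as stable or worsening pain responders".

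On timing of the pain score, Section 4.3 says "This will be performed prior to treatment and again at 1, 2, 3, and 6 months", so a nadir can come before month 3. On entry, Section 3.1.5 asks for a pain score of at least 5, "OR pain score < 5 with ≥ 60 mg of morphine (or equivalent) per day". Section 5.2.1 lists the secondary pain outcome as "Pain, on a 0-10 scale, and narcotic use, in daily oral morphine equivalents". It does not list the response category.

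**The concern.** The two rules measure change from different points: partial response presumably from baseline, progression from the lowest score reached. A patient who improves a great deal and then loses part of the gain can satisfy both. The residual class does not help, because it catches patients who meet no definition, not those who meet two. Neither Section 7.1 nor Section 11.2 says which rule wins.

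If *worsening* in Section 11.2 means progression in Section 7.1, such a patient fits both sides of the 3-month comparison. The labels add to the doubt: Section 11.2 speaks of *stable* patients, which is not a Section 7.1 class, and does not mention the indeterminate class. At stake would be the reported 3-month response rates and perhaps the p-value. Both could then turn on a coding choice made in a trial whose available text describes no blinding.

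**Working it through.** The plan gives no rate, sample size or power for this comparison, so there is no figure of its own to reproduce. The check has three parts.

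**1. Can both rules hold?** Write B for baseline, n for nadir and s for the month-3 score, with opioids unchanged.

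- Partial response, pain limb: B − s ≥ 2.
- Progression, first limb: s − n ≥ 2.
- Adding the two: B − n ≥ 4.

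Overlap therefore needs a fall of at least 4 points to the nadir, followed by a rise of at least 2 that still ends at least 2 below baseline. With B = 9, n = 3, s = 6, the fall is 9 − 6 = 3 and the rise is 6 − 3 = 3, so both hold. A complete response (s = 0) can never be a rise from nadir, so complete response and progression do not collide.

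**2. How much of the rule space overlaps?** For baseline B, count integer pairs (n, s) with n ≤ s.

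- Pairs meeting the partial-response rule: B(B − 1)/2.
- Pairs also meeting progression from nadir: (B − 2)(B − 3)/2.

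| Baseline | Meets partial-response rule | Also meets progression |
|---|---|---|
| 2 | 1 | 0 |
| 3 | 3 | 0 |
| 4 | 6 | 1 |
| 5 | 10 | 3 |
| 6 | 15 | 6 |
| 7 | 21 | 10 |
| 8 | 28 | 15 |
| 9 | 36 | 21 |
| 10 | 45 | 28 |
| Total 2–10 | 165 | 84 |
| Total 5–10 | 155 | 83 |

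One pair per baseline has s = 0 and is a complete response: 9 of the 165 and 6 of the 155. Without them the shares are 84/156 = 54% and 83/149 = 56%.

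These are counts of possible score patterns, not of patients, and the share depends on what is counted. Taking full paths through months 1, 2 and 3 for baselines 5 to 10, 1,491 of the 4,719 paths that meet the partial-response rule also meet progression, or 32%. None of these figures estimates how often overlap will happen. They show only that it is not confined to odd corners of the scale.

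**3. What could the coding do to the test?** Take 40 per arm (51 per arm and 20% loss from Section 11.3: 51 × 0.8 = 40.8). The responder counts are assumed. The test is taken as two-sided, because Section 11.2 does not say.

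| Overlap patients coded as | Overlap, 8/1 and 8/2 | Responders, 8/1 v 8/2 | Fisher p |
|---|---|---|---|
| Responders | any | 20/40 v 26/40 | 0.26 |
| Non-responders | 2 and 2 | 18/40 v 24/40 | 0.26 |
| Non-responders | 4 and 4 | 16/40 v 22/40 | 0.26 |
| Non-responders | 4 and 2 | 16/40 v 24/40 | 0.12 |
| Non-responders | 2 and 4 | 18/40 v 22/40 | 0.50 |

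Equal overlap lowers both rates by 5 or 10 points and leaves the p-value where it was. Movement comes only from unequal overlap, in a direction the documents do not let us predict.

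**Reading the two sections together.** Every patient with a baseline of 2 or more who reaches a score of 0 without more analgesic meets both complete and partial response. The Section 7.1 list therefore already has to be read from the top down to give each patient one class, and in that order partial response comes before progression. Section 11.2 names its first group in Section 7.1's own terms and its second group only loosely. The plain reading is complete or partial response at month 3 against everyone else. On that reading indeterminate patients fall in the second group and no patient is on both sides.

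**The case for a change.** The best case for a change is that none of this is written down. The top-down order is inferred. An analyst could equally let progression override response, and Section 6.2.1 itself treats a 2-point rise above nadir as a sign of worsening. This is the plan's only categorical test of pain response, and the exploratory models in Section 11.2 use a yes/no pain-relief outcome that is not defined separately. Two added sentences would cost almost nothing, and fixing the coding before arm-level data are seen is good practice in a trial with no blinding described.

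What stands is that the definitions are not mutually exclusive and that a written precedence would be tidier. What does not follow is that the analysis is unsound without it. The added sentence would record the coding most analysts would adopt anyway, so no result would change. A sensitivity table that counts overlap patients as non-responders would be an optional extra for a secondary analysis. It would also miss cases, because a missed interim score can hide the nadir. With baseline 9 and scores of 5, 3 and 6 at months 1, 2 and 3, losing the month-2 score moves the nadir from 3 to 5. The rise then shrinks from 3 points to 1, and the overlap disappears.

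**Conclusion.** The overlap exists on the text, but it is a gap that analysts fill sensibly. The claim that a patient belongs to both sides of the test needs *worsening* in Section 11.2 to mean progression in Section 7.1, which the plan does not say. Under the ordinary reading, responders against all others, a patient such as baseline 9, nadir 3, month 3 at 6 is a responder. Under the opposite reading, applied equally to both arms, the comparison is still valid and merely answers a stricter question.

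The size cannot be fixed from the documents. In the illustration p stays at 0.26 with equal overlap and ranges from 0.12 to 0.50 with a two-patient imbalance, all on assumed counts. The conclusion rests on two natural readings: that partial response is measured from baseline, and that Section 11.2 means responders against the rest. The primary re-treatment analysis, its power and the Section 5.2.1 outcomes do not depend on either. No change to the plan is called for.

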7.2 Radiation Induced Bone Changes

The patient will undergo standard of care CT simulation prior to treatment. No further imaging is required by the protocol. If the patient undergoes CT imaging after treatment for any reason, imaging will be analyzed for quantitative assessment of radiation-induced bone changes including bone mineral density and cortical. The date and type of imaging (if applicable) will be collected if it falls within the timeframes delineated in the follow-up assessment calendar (Section 6.1, attention to Footnote f). The scan data will be used for analyses comprising the exploratory objective delineated in Section 2.3. These results, if applicable, will be documented on Appendix K by the researchers after completion of the study.

8.0 Adverse Events List and Reporting Requirements

8.1 Adverse Event List for Radiation Treatment

Expected side effects, depending on the area treated, include nausea, vomiting, diarrhea, skin erythema and alopecia in the irradiated area, esophagitis, myelosuppression, urinary urgency and frequency, and pneumonitis.

8.2 Adverse Event Characteristics

- **CTCAE term (AE description) and grade:** The descriptions and grading scales found in the revised NCI Common Terminology Criteria for Adverse Events (CTCAE) version 4.0 will be utilized for AE reporting. All appropriate treatment areas should have access to a copy of the CTCAE version 4.0. A copy of the CTCAE version 4.0 can be downloaded from the CTEP web site (<http://ctep.cancer.gov>).
- **‘Expectedness’:** AEs can be ‘Unexpected’ or ‘Expected’ (see Section 7.1 above) for expedited reporting purposes only.
- **Attribution** of the AE:
 - Definite – The AE is **clearly related** to the study treatment.
 - Probable – The AE is **likely related** to the study treatment.
 - Possible – The AE **may be related** to the study treatment.
 - Unlikely – The AE is **doubtfully related** to the study treatment.
 - Unrelated – The AE is **clearly NOT related** to the study treatment.

8.3 DSMC SAE Reporting Requirements

The Data Safety Monitoring Committee (DSMC) is responsible for reviewing SAEs for WFBCCC Institutional studies as outlined in Appendix D. All Adverse Events that occur during protocol intervention and are coded as either 1) unexpected grade 4, 2) unplanned inpatient hospitalization \geq 24 hours (regardless of grade), or grade 5 (death) must be reported to the DSMC using the SAE console in WISER.

All WFBCCC Clinical Protocol and Data Management (CPDM) staff members assisting a Principal Investigator in investigating, documenting and reporting an SAE qualifying for DSMC reporting are responsible for informing a clinical member of the DSMC as well as the entire committee via the email notification procedure of the occurrence of an SAE.

8.4 WFUHS IRB AE Reporting Requirements

Any unanticipated problems involving risks to subjects or others and adverse events shall be promptly reported to the IRB, according to institutional policy. Reporting to the IRB is required regardless of the funding source, study sponsor, or whether the event involves an investigational or marketed drug, biologic or device. Reportable events are not limited to physical injury, but include psychological, economic and social harm. Reportable events may arise as a result of drugs, biological agents, devices, procedures or other interventions, or as a result of questionnaires, surveys, observations or other interactions with research subjects.

All members of the research team are responsible for the appropriate reporting to the IRB and other applicable parties of unanticipated problems involving risk to subjects or others. The Principal Investigator, however, is ultimately responsible for ensuring the prompt reporting of unanticipated problems involving risk to subjects or others to the IRB. The Principal Investigator is also responsible for ensuring that all reported unanticipated risks to subjects and others which they receive are reviewed to determine whether the report represents a change in the risks and/or benefits to study participants,

and whether any changes in the informed consent, protocol or other study-related documents are required.

Any unanticipated problems involving risks to subjects or others occurring at a site where the study has been approved by the WFUHS IRB (internal events) must be reported to the WFUHS IRB within 7 calendar days of the investigator or other members of the study team becoming aware of the event.

Any unanticipated problems involving risks to subjects or others occurring at another site conducting the same study that has been approved by the WFUHS IRB (external events) must be reported to the WFUHS IRB within 7 calendar days of the investigator or other members of the study team becoming aware of the event.

Any event, incident, experience, or outcome that alters the risk versus potential benefit of the research and as a result warrants a substantive change in the research protocol or informed consent process/document in order to insure the safety, rights or welfare of research subjects.

9.0 Blood Collection for Translational Research and Tissue Banking

In this study, if the patient consents, plasma and whole blood will be collected at baseline and post-treatment (3 months). We will explore promising genetic basis biomarkers with regard to of cancer-induced bone pain and cachexic syndrome following bone metastatic disease, since much work still remains to be accomplished in this area.

The whole blood collected will be utilized for microarray analyses or next generation RNA sequences. The pre-treatment and post-treatment (3 months) of plasma will be tested for a number of cytokines and proteins (e.g. calcitonin-gene related peptide (CGRP), substance P (SP), angiotensin II, Ang 1-7) that are thought to be predictive of cancer-induced bone pain and cachexic syndrome following bone metastasis disease.

This may lead to identification of promising new biomarkers with the goals of

1. Identifying factors predictive of outcome such that patients may be better stratified in future trials;
2. Developing novel treatment strategies which target the molecular abnormalities identified.

1) Blood Sample Preparation

1. Email notification will be sent to [REDACTED] the day before the blood collection.
2. Blood will be collected in green-top lithium-heparin or sodium-heparin vacutainer tubes (1 x 10 ml tube), and immediately inverted 8-10 times to prevent coagulation. **Attention: Protocol #: CCCWFU # 01416 should be on the tube**
3. Samples will then be sent to [name] lab ([name]) for research use. [name] lab [REDACTED]
4. Upon receipt, tubes will be centrifuged at 200 x g for 10 mins at room temperature with the break off.
5. Plasma will be removed and placed in 1.5ml Eppendorf tubes and transferred to the [name] lab and stored in -80 freezer until further processing. .

6. Buffy coat will be collected and placed in Eppendorf tubes in RNA later and transferred to the [name] lab, and stored in -80 freezer until further processing.

10.0 Data Management

Informed consent document	Wiser
Appendix A: Protocol registration form	Wiser
Appendix B: Subject Eligibility Checklist	Wiser
Appendix C: Race & Ethnicity Verification	Wiser
Appendix D: Mandatory DSMC SAE Reporting Guidelines	Wiser
Appendix E: Baseline data collection form	REDCap
Appendix F: Treatment data collection	REDCap
Appendix G: Patient Questionnaire	REDCap
Appendix H: Numerical Rating Pain Scale (NRPS)	REDCap
Appendix I: Adverse Events	Epic/REDCap
Appendix J: Retreatment Data Form	REDCap
Appendix K: Radiation Induced Bone Changes	REDCap

11.0 Statistical Considerations

11.1 Analysis of Primary Objective

This is a randomized Phase 2 study, with the primary objective to compare the 6-month cumulative incidence of re-treatment rates between groups. Based on previous research, the 8 Gy x 1 fraction [8/1] group (control group) had a retreatment rate of 18% (RTOG Study 97-14). The primary analysis will use a one-sided log-rank test statistic to test the null hypothesis that the re-treatment rates are equal in each group versus that alternative that the re-treatment rates are lower in the 8 Gy x 2 fractions [8/2] group. This analysis will account for competing risks such as death. Analyses will be performed on the patient level, thus if a patient has multiple metastases and any one of these requires retreatment then the patient will be considered retreated.

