11.3 Power and Sample Size

Power calculations were performed using PASS 13. When accounting for competing risks, a one-sided logrank test with an overall sample size of 102 subjects (51 in the control group and 51 in the treatment group) achieves 80% power at a 0.2 significance level to detect a hazard ratio of 0.5251. The study is expected to last for 42 months with an accrual (entry) time of 36 months and a follow-up time of 6 months after the last patient is accrued. The cumulative incidence proportions at time 3 months for the event of interest are 0.18 in the control group (8/1) and 0.10 in the treatment group (8/2). The cumulative incidence proportions at time 6 months for the competing risk factors are 0.20 in the control group and 0.20 in the treatment group. The proportion of subjects lost to follow-up during the entire study is conservatively estimated at 0.2.

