 HR is the hazard ratio (hev2/hev1), the treatment group's hazard rate divided by the control group's hazard rate for the event of interest.
 Fev1 and Fev2 are the cumulative incidences at time T0 for the event of interest in the control and treatment groups, respectively.
 Fcr1 and Fcr2 are the cumulative incidences at time T0 for the competing risk factors in the control and treatment groups, respectively.
 R is the accrual or entry time for the study.
 T-R is the followup time for the study. T is the total time.
 Alpha is the probability of rejecting a true null hypothesis. It should be small.
 Beta is the probability of accepting a false null hypothesis. It should be small.
 E is the total number of events required for the study.
 E1 and E2 are the number of events required for the control and treatment groups, respectively.
 Pr(ev) is the overall probability of observing the event of interest during the study.
 Pr(ev1) and Pr(ev2) are the probability of observing the event of interest in a subject during the study for the control and treatment groups, respectively.
 hev1 and hev2 are the hazard rates for the event of interest in the control and treatment groups, respectively.
 hcr1 and hcr2 are the hazard rates for the competing risk factors in the control and treatment groups, respectively.
 Rpt Row is a line number assigned to allow corresponding report lines to be identified.

2/23/2016 10:03:19 AM 2

Logrank Tests Accounting for Competing Risks

Summary Statements

When accounting for competing risks, a one-sided logrank test with an overall sample size of 102 subjects (51 in the control group and 51 in the treatment group) achieves 80.195% power at a 0.200 significance level to detect a hazard ratio of 0.5251. The study lasts for 24 time periods with an accrual (entry) time of 18 periods and a followup time of 6 periods. The cumulative incidence proportions at time 3 for the event of interest are 0.1800 in the control group and 0.1000 in the treatment group. The cumulative incidence proportions at time 3 for the competing risk factors are 0.2000 in the control group and 0.2000 in the treatment group. The proportion of subjects lost to followup during the entire study is 0.2.

Logrank Tests Accounting for Competing Risks

File View Run Procedures Tools Window Help

Reset Open Save As

Calculate

Design

Design Solve For: Sample Size

Reports

Plots

Plot Text

Test

Alternative Hypothesis: One-Sided

Power and Alpha

Power: .8

Alpha: .2

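### Section 11.1 sets a 6-month cumulative incidence objective but names a log-rank test without giving the competing-risks method or a 6-month cut; the sizing run points to a comparison of cause-specific hazards

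*Combined protocol and SAP*

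**What the plan says.** Objective 2.1.1 and outcome 5.1.1 ask about cumulative re-treatment by 6 months after treatment completion. Section 11.1 repeats this as the "primary objective to compare the 6-month cumulative incidence of re-treatment rates between groups". The test follows: "The primary analysis will use a one-sided log-rank test statistic to test the null hypothesis that the re-treatment rates are equal in each group". On deaths there is one sentence: "This analysis will account for competing risks such as death". Section 11.1 names no test variant, rule for deaths, incidence estimator, confidence interval or truncation time.

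Section 11.3 sizes the trial so that it "achieves 80% power at a 0.2 significance level to detect a hazard ratio of 0.5251". The software output printed after section 11.6 defines that ratio: "HR is the hazard ratio (hev2/hev1), the treatment group's hazard rate divided by the control group's hazard rate for the event of interest". The run uses 18 months of accrual plus 6 of follow-up, so it counts events to 24 months.

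On follow-up length, section 11.5 gives every patient 6 months and section 6.2.1 records re-treatment at the 6-month visit. Footnote f of section 6.1 lets that visit fall anywhere from week 20 to week 34, and section 6.4 treats 6 months as a minimum. Appendix J records the date of the first re-treatment.

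**The concern.** Cumulative incidence of re-treatment depends on two rates: how fast patients are re-treated and how fast they die or otherwise become unable to be re-treated. An unmodified log-rank test drops patients from the risk set at death and compares only the first rate. The two null hypotheses coincide when competing hazards are equal and hazards are constant, but not in general.

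If 8 Gy x 2 changed mortality, or selected patients with different mortality, the primary p-value could answer a different question from objective 2.1.1. If events were also counted beyond 6 months, as in the sizing, the test would cover a longer period than the endpoint. Competing events are not rare here: the sizing inputs imply about one-third of patients by 6 months.

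**Working it through.** **1. Reproduce the plan's figure.** Inputs from the software output: re-treatment incidence 0.18 and 0.10 and competing incidence 0.20 and 0.20, all at T0 = 3 months; accrual 18; follow-up 6; loss 0.20; one-sided alpha 0.20; N = 102.

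Total hazard = -ln(1 - Fev - Fcr)/T0, split in proportion to Fev and Fcr.
- Control: -ln(0.62)/3 = 0.1593, giving 0.0755 (event) and 0.0839 (competing).
- 8/2: -ln(0.70)/3 = 0.1189, giving 0.0396 and 0.0793.
- HR = 0.0396/0.0755 = 0.5251 (unrounded inputs), as printed.

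With total hazard L, the event probability is (hev/L) x [1 - (e^(-6L) - e^(-24L))/(18L)] = 0.4138 and 0.2660, mean 0.3399, all as printed. Events = 102 x 0.3399 x 0.8 = 27.7 (printed 27.5). Power = Phi(sqrt(27.7) x 0.6443/2 - 0.8416) = 0.804 (printed 0.80195). So the printed power belongs to a cause-specific hazard comparison with events to 24 months.

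**2. Incidences at 6 months from these hazards.** F(6) = (hev/L)(1 - e^(-6L)).
- Control: re-treatment 0.6156 x 0.18/0.38 = 29.2%; competing 0.6156 x 0.20/0.38 = 32.4%.
- 8/2: re-treatment 0.51 x 0.10/0.30 = 17.0%; competing 34.0%.

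**3. Level when 6-month incidence is equal.** Trials were simulated with 51 per arm, no losses, one-sided 0.20 and a 6-month cut. Control hazards are as above. The 8/2 competing hazard is set to 0.05 or 0.12 (ratios 0.05/0.0839 = 0.60 and 0.12/0.0839 = 1.43). The 8/2 event hazard is then solved so that F(6) = 29.2% in both arms. These ratios are assumptions; the documents give none.

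| Competing-hazard ratio | Cause-specific HR | Competing incidence in 8/2 | Log-rank, deaths censored | Gray's test |
|---|---|---|---|---|
| 0.60 | 0.90 | 21.5% | 29% | 20% |
| 1.00 | 1.00 | 32.4% | 20% | 20% |
| 1.43 | 1.12 | 41.5% | 13% | 20% |

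**4. Sensitivity to the competing rate.** Section 11.3 places the 0.20 competing incidence at 6 months; the software run places it at 3. With 0.18 re-treatment at 3 months and 0.20 competing at 6, the log-rank rejects about 26% and 16% at the same two ratios. With both at 6 months, it rejects about 24% and 17%.

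**5. The cut.** Letting follow-up end anywhere in weeks 20 to 34 moves the log-rank rejection rate by at most about 1 point. Following to 24 months matters more. If hazards are equal to 6 months and the 8/2 re-treatment hazard halves afterwards (an assumed pattern), the log-rank rejects 37%, against 20% with a cut. Gray's test also needs the cut: followed to 24 months, it ranges from 10% to 37% for death hazard ratios of 0.5 to 2.

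**6. Power with the cut.** Events = 51 x (0.2916 + 0.17) = 23.5, so the log-rank has Phi(sqrt(23.5) x 0.6443/2 - 0.8416) = 76%. Simulated power is 76% for the log-rank and 74% for Gray's test without losses, and 74% and 72% with 20% of patients lost at a random time in follow-up. The sizing formula's cruder convention (events x 0.8 = 18.8) gives 71% for the log-rank.

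**The case against.** The strongest reply is that no sentence says deaths are censored. Section 11.1 says the opposite in spirit, and a sizing routine does not define an analysis. This stands: a reader might infer that the plan will censor deaths, but the documents support only an unspecified method whose one technical clue is cause-specific.

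Second, the 6-month horizon appears in 2.1.1, 5.1.1, 11.1 and 11.5, and the Appendix J date allows truncation. This also stands in part. If follow-up ends by week 34, late events hardly matter; what is missing is the explicit rule.

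Third, a reader might infer that a chance imbalance in deaths inflates the error rate. It does not: with equal true competing hazards, which is the plan's assumption, the level is 20%. A real difference in hazards is needed, and the departure can go either way.

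Fourth, Gray's test has its own awkward case. With equal re-treatment hazards and a competing hazard 1.43 times higher in 8/2, it favours 8/2 about 29% of the time, against 20% for the log-rank. For this objective that is not a false positive, because 6-month incidence really is lower there. It would still be a poor clinical result, which is why the cause-specific test should stay as support.

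Finally, a reader might fear inflated estimates from treating deaths as censored, 1 - e^(-6 x 0.0755) = 36% and 1 - e^(-6 x 0.0396) = 21% instead of 29% and 17%. No passage proposes that estimator.

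**Conclusion.** The point holds as a mismatch between objective and named test, made worse by missing specification. It is not a demonstrated error in the level of the test. Under the plan's equal competing incidence the log-rank is valid at 20%. The departures to about 29% or 13% rest on three assumptions: deaths are censored, competing hazards differ by ratios of 0.60 or 1.43, and the software inputs apply. They shrink to about 24-26% or 16-17% if the competing incidence is 0.20 at 6 months.

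The effect on stated power does not depend on unequal mortality. The printed 80% relies on events after 6 months, which the stated endpoint excludes. This should be corrected before outcome data are analysed.

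**What to change.** In section 11.1:
- Truncate each patient's data at 6 months after treatment completion, using the Appendix J date of first re-treatment.
- Make Gray's test the primary test, one-sided at 0.20 through its signed two-group form, with death as a competing event.
- Report Aalen-Johansen 6-month incidence per arm and the difference with a confidence interval. Gray's test compares whole curves, so this difference is what answers objective 2.1.1 directly.
- Keep the cause-specific log-rank as a supporting analysis, to show whether any difference is driven by deaths.

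In section 11.3, restate power for the 6-month cut: about 74% without losses and about 72% with 20% loss under the software inputs, with the loss convention stated. About 2 points of the fall from 80% come from using Gray's test; the rest comes from no longer counting events after 6 months.

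The cost is SAP wording and an honest, lower power figure. No new re-treatment field is needed. Dates of death and last contact are required, as for any competing-risks analysis.
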